## 10 DEVICE MALFUNCTIONS

A device malfunction means the failure of the device to meet its performance specification or otherwise perform as intended. Any defective lens that is *likely* to cause or contribute to a *Serious Adverse Event* should be reported to CORE and the sponsor **within 24 hours** of the investigator becoming aware of the malfunction. The ORE would also be notified within 24 hours of any device malfunction that may contribute to a *Serious Adverse Event*.

Other defective lenses should be reported to CORE as soon as possible (usually in weekly study updates).

This clinical study will also ascertain satisfaction or preference with subjective attributes such as comfort, vision, or lens handling. Responses to these subjective questionnaires will not be considered as complaints or device malfunctions.

## 11 STUDY COMPLETION AND REMUNERATION

At the last scheduled protocol visit a study completion form will be completed, which requires the signatures of both the participant and the investigator. Participants will also be provided with a letter of appreciation.

Once their involvement in the study is complete, participants will be informed about receiving feedback following study completion in the Letter of Appreciation.

Participant remuneration will be approximately US\$165 for completing the study. This is calculated at \$20 per hour for the 1 hour of at home ratings questionnaires and 7.25 hours of predicted scheduled visits, though if additional fitting time is required, this may increase.

## 12 STATISTICAL ANALYSIS AND DATA MANAGEMENT

### 12.1 STATISTICAL ANALYSIS

All data will be analyzed by CORE at the University of Waterloo. Unmasked data analysis will be conducted using Statistica 10, Statsoft or other suitable software. Descriptive statistics will be provided on demographic data (age, gender, refractive error distribution, etc.). Table 7 lists the primary and other outcome variables and anticipated statistical procedures.

Comparisons will be made between the study lenses for the variables measured at the 2-week visits. Additionally the subjective ratings completed on day [REDACTED] 13 of each phase will be compared. A binomial test will be used to analyze the results for the count data [REDACTED]  
[REDACTED] Where relevant, the number of “neither agree or disagree” responses will be evenly distributed to the two options on the basis they would be equally likely to choose either.

Where appropriate, data may be presented as both mean and as counts by ‘bucket’ groups.

Table 6: Statistical procedures

Variable	Analysis	Statistical test
Ratings: Likert & Preference	Comparison between study days and/or between contact lenses per time point.	Freidman ANOVA Wilcoxon matched pairs test
Ratings: numerical ratings Biomicroscopy	Comparison between study days and/or between contact lenses per time point.	Freidman ANOVA Wilcoxon matched pairs test RMANOVA
Demographics Lens fit variables	Descriptive stats	One or more: mean, median*, mode, standard deviation, minimum, maximum, frequency count

\* For non-parametric data only

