## 2 INTRODUCTION

Multifocal contact lenses provide correction for vision at near as well as in the distance. This segment of the contact lens market has been slowly growing as more products become available.

CooperVision is interested in comparing the performance of their newly developed daily disposable (DD) MyDay® Multifocal (Lens A) contact lens to patients' habitual multifocal lenses and to the competitor product DAILIES TOTAL1® Multifocal (Lens B). Of particular interest is the comparison of handling the lenses, which includes insertion and removal to and from the eye. Ease of lens handling is critical in a presbyopic population who require specific prescription for seeing well up close.

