## 5 MATERIALS AND METHODS

### 5.1 STUDY DESIGN

#### 5.1.1 OVERALL DESIGN

This is a prospective, randomized, participant-masked, crossover, bilateral dispensing study conducted at up to 5 clinical practice sites in the United States, listed on page 3. Each lens type will be worn for up to 3 weeks. The lens prescription of each lens type will be optimized after 3-7 days wearing experience, prior to starting a 2-week wear period.

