#### 5.1.2 RANDOMIZATION

Participants will be wearing their habitual lenses during the first 2-week phase, followed by a randomized order of Lens A and Lens B lens wear.

A randomization schedule will be generated for each site using a web-based program to determine the order of Lens A and Lens B lens wear: ([www.randomization.com](http://www.randomization.com)). The final study randomization schedule will be generated by CORE's Database Administrator and provided to the research assistants at each site.

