### 5.1.3 MASKING

---

Participants will wear their habitual lens with an optimized prescription during the first Phase, followed by a masked lens wear using Lens A and Lens B. Lens packages/foils will be over-labeled with strongly adhesive stickers to mask the participant to the lens brand.

It is not possible for the study investigators to be masked because of the need to follow the specific lens fitting guide during the lens prescription optimization visit (Visits 0, 2-1, 3-1).

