## 12.3 COMMENTS ON SOURCE DOCUMENTS

Data analysis will not be conducted on comments which have been recorded in the source documents. Only relevant and applicable comments will be included in the final report as deemed necessary by CORE's Lead Co-ordinator.

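### Section 12.1 plans an unmasked analysis although the planned tests do not need lens identity, while two choices that can affect the primary Lens A versus Lens B result stay open until data are in hand

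*Combined protocol and SAP*

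**What the plan says.** The trial describes itself in section 5.1.1 in these terms: "This is a prospective, randomized, participant-masked, crossover, bilateral dispensing study". Section 5.1.3 explains why the other party at the sites is open: "It is not possible for the study investigators to be masked because of the need to follow the specific lens fitting guide". It gives no reason that concerns analysts.

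Section 12.1 places the analysis at the coordinating centre, "All data will be analyzed by CORE at the University of Waterloo", and continues: "Unmasked data analysis will be conducted using Statistica 10, Statsoft or other suitable software". No section provides for coded lens labels, a masked review of the data, or settling the analysis population before lens identity is known. The letters A and B give no cover, because section 2 decodes them: the sponsor's product is the "newly developed daily disposable (DD) MyDay® Multifocal (Lens A) contact lens".

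On custody of the allocation, section 5.1.2 says: "The final study randomization schedule will be generated by CORE's Database Administrator and provided to the research assistants at each site".

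Two choices are left open. Section 5.5 makes out-of-window visits protocol deviations and defers to the end of the study, without a rule, the question of whether their data join the analysis population. Table 6 in section 12.1 lists Friedman ANOVA, the Wilcoxon matched pairs test and RMANOVA for numerical ratings, and the text calls the procedures anticipated. None is named for the primary comparison. Section 5.3.1 sized the study on a two-tailed t-test.

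**The concern.** The primary comparison sets the sponsor's new lens against a competitor's on a subjective 0-10 handling rating. Investigators are open for a practical reason. Nothing practical requires the analyst to be: a paired comparison of the two lenses runs equally well on codes X and Y.

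An open analyst would be harmless if every step after data collection were fixed. Here the analysis population and the test can both be settled with the ratings and lens labels in view. Either choice could then lean towards one lens without anyone intending it, and the sponsor would have no procedural answer to that criticism.

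**Working it through.** **1. The plan's own figure.** Inputs from section 5.3.1: SD 12.7 and target difference 5 (0-100 scale), 80% power, two-sided alpha 0.05. The normal approximation gives (12.7 × (1.960 + 0.842) / 5)² = 7.117² = 50.7, so 51. With the noncentral t for a paired comparison, the smallest n with power of at least 0.80 is 53 (power 0.803); 60 participants give 0.851. The stated 53 is reproduced. Masking the analyst changes none of these inputs.

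**2. Is lens identity needed?** Wilcoxon, Friedman, RMANOVA and the binomial test each need to know which ratings share a lens, not which brand it is. Table 2 already organises visits by Pair #1 and Pair #2, with identity supplied by the randomization table.

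**3. Which steps can affect the primary result?**

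| Step | Section | Can it affect the primary A-B result? |
|---|---|---|
| Data from out-of-window visits | 5.5 | Yes, if Day 13 ratings linked to such visits are included or dropped |
| Test for numerical ratings | 12.1, Table 6 | Yes, through the p-value |
| Grouped counts | 12.1 | No, shown in addition to the mean |
| Comments reported | 12.3 | No, not analysed |
| Unclear ratings | 5.5.4, 14 | Little: checked at the visit, entered by two people, queries sent to the site |
| Primary variable and day | 3 | No, fixed |

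Two cautions apply. Section 5.5 does not say whether a Day 13 home rating returned at a late visit counts as data from a deviation. Table 6 puts numerical ratings and biomicroscopy in one row, so the three tests are read as applying to both.

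**4. How much room do the two open choices leave?** This is an illustration on assumptions that are not in the documents: no true difference, n = 53, integer 0-10 ratings with mean 8, between-person and within-person SD 0.9 each, 6,000 runs per setting. The three tests were a paired t-test (equivalent to RMANOVA for two lenses), Wilcoxon and a two-lens Friedman test.

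- One fixed test: type I error about 0.05.
- Smallest p-value of the three: about 0.07.
- Also choosing whether to keep deviation data: 0.0867, 0.0905 and 0.1008 when 5%, 10% and 20% of participants have deviations.

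**5. How much of that is due to open labels?** The search in step 4 is symmetric, and an analyst seeing only X and Y could do the same. A second run on the same assumptions separated direction. Its symmetric search gave 0.075 for the tests alone and up to 0.099 with deviation data, so false wins for Lens A were half of that: 0.0375 to 0.0495. When every choice was instead made in favour of Lens A, false wins for Lens A were 0.04 to 0.05, against 0.025 for one fixed test. Total error stayed near 0.05 to 0.06, leaving about 0.01 for false wins for Lens B. Open labels therefore add asymmetry between the lenses. The inflation itself comes from the unfixed test and population rule.

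**The case against.** The strongest reply is that this is a disclosed design choice with little to act on. The trial claims only participant masking and says openly that the analysis is unmasked. The primary value is an integer chosen by a masked participant on a fixed day, and data are entered by two people and compared. All of this stands, and it limits the effect.

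A reader might infer that every judgement at the coordinating centre is made with Lens A and Lens B labelled. The documents do not say so. Section 12.1 applies the word unmasked to the data analysis only. Visits are coded by phase and pair, the home rating forms go to masked participants, and section 12.2 leaves details of data handling and personnel to a separate data management plan. What can be said is that no step there is stated to be protected by masking.

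A reader might also point to discretion over comments, "Only relevant and applicable comments will be included in the final report as deemed necessary by CORE's Lead Co-ordinator", or to the grouped counts. Neither enters the primary mean.

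It is also tempting to size the bias by supposing that the A-B difference moves by one point in 5 of 53 participants. That gives 5/53 = 0.094, against a standard error of 1.27/√53 = 0.174 on the 0-10 scale: 0.54 of a standard error, or 19% of a 0.5-point difference. The arithmetic is right, but the documents show no route by which recorded integers would be changed.

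Finally, masking all data review would not be cheap. Sites send all visit documents to the centre, the lens order form is in the visit pack, and the centre coordinates Lens A orders and reconciles dispensing logs (sections 5.2.2 and 5.4). A deviation such as an incorrect lens dispensed cannot be judged without lens identity. This objection stands and narrows the remedy.

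**Conclusion.** The point holds in a limited form. Section 12.1 chooses an unmasked analysis without a reason, the reason given for investigators does not carry over, and two choices that can affect the primary A-B result remain open once data are in hand. No bias can be sized from the documents. The simulated error rates rest on assumed rating distributions and deviation rates, describe the case where every choice is exploited, and mostly measure missing pre-specification. What coding removes is the tilt towards one lens. Sample size, alpha, power and visits are unchanged. This is a cheap improvement, not a defect that undermines the trial.

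**What to change.** Replace the sentence on unmasked analysis in section 12.1, keeping the software name, with wording such as:

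*Decisions on including data from visit-window deviations, the choice of primary test, and the primary Lens A versus Lens B analysis will be made on a dataset in which the two study lenses carry neutral codes (X and Y). The Database Administrator holds the key and releases it after database lock and after the primary result has been produced.*

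Habitual-lens data, operational data review, site queries and deviations that concern lens identity may stay labelled. Fields that reveal the lens, such as base curve (8.4 or 8.5 mm in Table 1), should be left out of the coded dataset.

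The cost is one recoded variable, and the analyst must not be someone who handles lens orders or dispensing logs. The Database Administrator already generates the schedule, so a key-holder exists. Separately, name one primary test and write the rule for deviation data before the code is broken; coding does not replace either.

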## 3 OBJECTIVES

The objective of the study is to compare the lens handling and performance of Lens A to habitually worn multifocal contact lenses and to the competitor Lens B.

The primary outcome variable for this study is:

- Subjective at-home ratings of 'Lens handling for insertion', using a 0-10 scale, collected on Day 13.

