## 5.3 STUDY POPULATION

### 5.3.1 SAMPLE SIZE CALCULATION

The sample size was calculated using lens handling data from a previous study comparing Lens A against lens B (CooperVision, data on file). In that study a 0-100 scale was used, not the 0-10 used in this study. As a way of compensating for fewer step sizes in the 0-10 scale, a target difference of 5 units on the 0-100 scale was chosen as a meaningful clinical difference in 0-100 subjective responses.

Using the 0-100 scale data described above for 'lens handling for insertion', where the data showed a standard deviation of 12.7 and when applying requirements of 80% power and alpha 0.05 in a two-tailed t-test, a minimum sample size of 53 participants is recommended in order to detect a mean difference of 5 units.

To account for dropout, up to 60 participants may be randomized and dispensed with study product in total, with the target of at least 53 completing the study.

Note: this study will use a subjective rating scale of 0-10, integer steps.

[figure not shown]

Figure 1: Sample size calculation graph

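### Splitting neutral responses evenly makes the section 12.1 binomial test conservative for non-primary count items, if the split counts enter the test and its null is 50:50

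*Combined protocol and SAP*

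**What the plan says.** Section 12.1 states: "A binomial test will be used to analyze the results for the count data". The rest of that sentence is blacked out. The next visible sentence, limited to cases where it is relevant, says that neutral "responses will be evenly distributed to the two options on the basis they would be equally likely to choose either". A separate short paragraph then turns to display: "data may be presented as both mean and as counts by" grouped categories.

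Table 6 in the same section does not list the binomial test. For Likert and preference ratings it gives "Freidman ANOVA Wilcoxon matched pairs test". Section 10 confirms that such items are collected: "This clinical study will also ascertain satisfaction or preference with subjective attributes such as comfort, vision, or lens handling".

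The primary outcome is of another kind. Section 3 defines it as "Subjective at-home ratings of 'Lens handling for insertion', using a 0-10 scale, collected on Day 13". Section 5.3.1 sizes the trial on that rating: "up to 60 participants may be randomized and dispensed with study product in total, with the target of at least 53 completing the study".

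**The concern.** A rule that turns three response categories into two counts looks like preparation for a test of two counts. If it is, the neutral responses enter the denominator as observations but contribute no random variation. The stated rationale does not justify this. Neutral respondents who really chose at random would sometimes favour one option and sometimes the other, whereas a fixed half-and-half split removes that variation.

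At stake is the chance of detecting a real imbalance among participants who hold an opinion. Under this reading such an imbalance is more likely to be reported as non-significant, and increasingly so as the neutral share grows.

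**Working it through.** **Inputs from the documents.** A binomial test and an even split (section 12.1); 53 completers targeted and at most 60 randomized (section 5.3.1). The plan gives no power or error rate for the binomial test, so there is no figure of its own to reproduce on this point. The sample size does reproduce: a paired t-test with difference 5, SD 12.7 (taken as the SD of the paired difference) and two-sided 0.05 has power 0.795 at n=52 and 0.803 at n=53. It rests on the primary rating alone.

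**Assumptions not in the documents.** Null of 50:50 between the options; two-sided exact test at 5%; neutral share q from 5% to 40%; 70:30 preference among deciders for power; every completer answers the item.

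**Mechanism.** Let A and B be the counts choosing each option, d = A + B, t neutrals and n = d + t. The split count is X = A + t/2.

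- Its distance from the null is unchanged: X − n/2 = A − d/2.
- Its null variance is d/4, because t/2 is fixed given t. The test assumes n/4.
- The standardised statistic is therefore that of the deciders multiplied by √(d/n).
- Large-sample type I error is 2(1 − Φ(1.96/√(1 − q))). For q = 0.20, 1.96/√0.80 = 2.19, giving 2.8%. For q = 5, 10, 30 and 40% it is 4.4, 3.9, 1.9 and 1.1%.

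**Exact enumeration at n=53**, with deciders ~ Binomial(n, 1 − q), choices ~ Binomial(d, p), and an odd neutral dropped:

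| Neutral share | Type I error, split | Type I error, deciders only | Power, split | Power, deciders only | Loss (points) |
|---|---|---|---|---|---|
| 5% | 2.8% | 3.9% | 76% | 80% | 4 |
| 10% | 2.4% | 3.7% | 72% | 77% | 5.5 |
| 20% | 1.7% | 3.6% | 60% | 71% | 11 |
| 30% | 1.05% | 3.4% | 46% | 64% | 18 |
| 40% | 0.57% | 3.1% | 30% | 55% | 25 |

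Part of the shortfall from 5% is discreteness of the exact test: with no neutrals at n=53 the type I error is already 2.7%.

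**Sensitivity to n.** n=53 is near the unfavourable end. Over n=53 to 60, with an odd neutral dropped, the loss is 0.1–3.9, 1.3–5.5, 6.2–11.4, 12.8–18.4 and 20.4–26.4 points at 5, 10, 20, 30 and 40% neutral.

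**Sensitivity to an odd neutral.**

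- Spare given to the leading option: at n=53 the rejection rates equal those in the table. At n=56 and n=58 with 10% neutral, the split has 0.8 and 2.0 points more power than deciders only. At n=58, type I error reaches 5.3% at 2% neutral and 5.0% at 5%. No other n from 53 to 60 exceeded 5% at the shares examined.
- Spare given to the trailing option: the loss at n=53 is 9, 11, 18, 25 and 31 points.

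**Single results (two-sided exact p).**

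- 31 v 16 with 6 neutral: 0.040 on deciders; 0.053 as 34 of 53.
- 29 v 14 with 10 neutral: 0.032; 0.053 as 34 of 53.
- 23 v 10 with 20 neutral: 0.035; 0.098 as 33 of 53.
- Reverse direction, 34 v 19 with 1 neutral: 0.053; 0.040 as 35 of 54.

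With 20 neutrals at n=53, the leader needs 23 of 33 deciders (70%) to reach p ≤ 0.05 without the split and 25 of 33 (76%) with it.

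**The case against.** The strongest reply is that the link to the test is not visible. The binomial sentence breaks off at a redaction, the split sentence follows further hidden text, and the next paragraph is about display. If the split serves only displayed percentages, there is no testing error. This stands as a limit on certainty: a reader might infer that the plan definitely tests the split counts, and the visible text does not establish that. Nor can the plan be faulted for lacking a rule for an odd neutral, since one may be blacked out.

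A second reply is that the null is not visible. The response wording suggests agree/disagree items, where the question could be whether a majority of all respondents agree. If exactly half of all respondents truly agree, then at n=53 with 10, 20 and 30% neutral, false rejection towards agreement is about 7, 22 and 53% with the split (odd neutral dropped), and about 9, 32 and 71% on deciders only. For such an item the split is far from conservative and dropping neutrals is worse. This stands as a limit on scope. It does not defeat the point for two-option items. An even split tests whether P(A) + P(neutral)/2 = 0.5, which is the same as P(A) = P(B), or 50:50 among deciders. That also fits the plan's rationale, so dropping neutrals there keeps the hypothesis and corrects the variance.

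Third, Table 6 lists Friedman and Wilcoxon tests for Likert and preference ratings, so the binomial test need not be the only inference on these responses. That also stands.

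**Conclusion.** The point holds conditionally. If the split counts enter the binomial test and the null is 50:50 between two options, the test uses too large a variance and is conservative, with small exceptions when an odd neutral is given to the leader. Under the assumptions above, the loss at n=53 is about 4 to 11 points of power at 5–20% neutral and 18 to 25 points at 30–40%. At some n from 54 to 60 with few neutrals it is negligible or reversed. Nothing in the documents gives the expected neutral share, so the trial cannot be placed within that range.

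A reader might infer that the trial's main comparison is weakened. It is not: the primary outcome is a numerical rating "using a 0-10 scale, collected on Day 13", and the sample size rests on that rating. A reader might also infer that the split can never help a claim of difference; the 34 v 19 example and the n=58 result show otherwise. The mechanism is certain under the stated null. That the split feeds the test is likely but unconfirmed. Minor priority.

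**What to change.** In section 12.1, replace the even-split sentence with text to this effect: *For items tested against a 50:50 null between two options, the two-sided exact binomial (sign) test will be run on participants who chose one of the two options. The number and percentage of neutral responses will be reported beside each result. Any even split of neutral responses is for displayed percentages only.*

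If an item asks whether a majority of all respondents agree, say so, keep all respondents in the denominator and do not count neutrals as agreement. Neither splitting nor dropping neutrals is valid for that question.

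The cost is a few lines of text, with no change to data collection or sample size. The drawback is that the two-option test describes only those with an opinion. For example, 12 v 3 with 38 neutral gives p=0.035 although 38/53 = 72% had no opinion (the split would give p=0.27 as 31 of 53). The neutral share must therefore accompany every result.
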